6.8. Concomitant Medications

All medications and supportive therapy taken within four weeks prior to Cycle 1, Day 1 and through 28 days after last study treatment must be recorded on the appropriate electronic case report form (eCRF). The identity of all medications, dosage, and route of administration, frequency, duration of administration, and indication for use will be recorded in the appropriate sections of the eCRF.

Prior and concomitant medications will be coded using the September 2015 or later version of World Health Organization drug dictionary (WHO Drug). Separate summary tables will be provided for prior and concomitant medications. Summary tables will be organized to display the anatomical main class of each coded medication (ATC level 1 term) and, within that, the pharmacological subgroup (ATC level 3 term) of the coded medication. The summary table will display counts and percentages of patients who reported using at least 1 medication in each represented pharmacological subgroup. If a patient has more than one medication in the subgroup, they will be counted only once. A complete listing will be generated as well.

6.9. Concomitant Procedures

All procedures within four weeks of Cycle 1, Day 1 and through 28 days after last study treatment must be recorded on the appropriate electronic case report form (eCRF). Concomitant procedures will be coded using MedDRA (version 18.1 or later), associating lower-level terms with preferred terms and system organ classes by the primary hierarchy. Complete listings of these data will be generated.

6.10. Ophthalmic Examinations

Results of the Ophthalmic Examinations will be presented in data listings.

6.11. Ocular Symptom Assessments

Results of the Ocular Assessments will be presented in data listings.

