11.1. Sample Size

Ascending doses of IMGN853 are to be evaluated to identify the MTD for both dosing schedules. The actual number of patients accrued during this phase will be determined largely by the findings observed during the course of their treatment.

Following identification of the MTD for Schedule A (Q3W), there was an expansion phase which initially accrued two cohorts at the MTD: (1) Dose Expansion Cohort 1-40 patients with platinum resistant EOC. (2) Dose Expansion Cohort #2-20 patients with advanced or recurrent uterine cancer. Once the Schedule B MTD (modified weekly) was established, the CRC convened to review safety, PK and efficacy results from the both schedules as well as preliminary data from the Expansion Cohorts 1 and 2, with the Q3W schedule of administration. The CRC recommended use of Schedule A for all future cohorts. Three additional MTD Expansion Cohorts will enroll the following patients: (3) Dose Expansion Cohort 3-20 patients with relapsed ovarian cancer, which is amenable to biopsy (4) Dose Expansion Cohort 4-20 patients with relapsed/refractory NSCLC adenocarcinoma, and (5) 40 patients with platinum resistant EOC who will receive daily treatment with corticosteroid-containing eye drops.

If the true DLT rate at the MTD is 10-20%, there is an 98.5-99.9% probability of observing at least one DLT in each 40 patient cohort. If the true response rate at the MTD is 20%, there is a 99.9% probability of observing at least one response in each 40 patient cohort.

ImmunoGen, Inc. Confidential Page 106 of 138

x (Number	True Event Rate			
Observed)	10%	20%	30%	
1	0.985	0.999	0.999	
2	0.919	0.998	0.999	
3	0.777	0.992	0.999	
4	0.577	0.972	0.999	
5	0.371	0.924	0.997	
6	0.206	0.838	0.991	

Table 16: Probability of Observing $\geq x$ Events (Response or DLT) For a 40 patient Cohort

Given a sample size of 40 patients, the power to detect a difference of 20% (rate of Blurry vision decrease from 50% to 30%) is 68% using one-sided alpha of 20% and Chi-Square test statistics.

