- a. Within 28 days prior to the start of Cycle 1, Day 1
- b. Directed physical examination is acceptable while on study treatment. Full examination is required at screening and the 28-Day Follow Up visit.
- c. Within 14 days prior to the start of Cycle 1, Day 1
- d. Vital signs (blood pressure, pulse, respiration rate, and temperature) will be measured as outlined in Section 8.6 and 8.7.
- e. Pulmonary Function Tests will be performed within 14 days of receiving the first dose of study treatment (Cycle 1 Day 1) and as clinically indicated.
- f. Day 1 laboratory assessments may be performed up to 4 days prior to study agent administration. Laboratory results must be reviewed prior to each scheduled administration of IMGN853. In the event of severe toxicity, repeat laboratory tests should be performed as necessary until the toxicity resolves or stabilizes. For a complete list of laboratory assessments, refer to Section 8.10.
- g. For WCBP, a urine or serum pregnancy test will be performed at screening, prior to dosing on Day 1, every-other-cycle while on study and at the 28-day Follow-Up visit. Additional testing may be performed in accordance with institutional requirements or local regulation.
- h. Baseline ophthalmic exams will be performed by a board-certified ophthalmologist and will include the following: indirect fundoscopy, slit lamp examination under dilatation, intraocular pressure measurement, and corneal photography. A Schirmer test will be performed at baseline for all patients, and for patients who experience ocular symptoms, it will be repeated at the first on-study ophthalmic examination and at subsequently if clinically indicated. The baseline exam may be performed within 14 days of Cycle 1, Day 1. Ocular symptom assessment will be performed prior to the start of each cycle by the treating physician or other qualified individual. If the subject reports ocular symptoms then IMGN853 will be stopped and the subject will then be referred to an ophthalmologist for a complete examination (Section 5.8.8).Patients who experience ocular toxicity will have a complete ophthalmologic exam performed every other cycle, including patients with blurred vision but normal eye examinations. All patients will have a complete ophthalmologic exam performed at the End of Treatment visit or 28-Day Follow Up.

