2.1.2. Secondary

- Evaluate the safety and tolerability of IMGN853
- Evaluate the effectiveness of primary, prophylactic steroid eye drops in preventing or lessening keratopathy and/or blurred vision
- Characterize the PK of IMGN853 when administered intravenously
- Describe any preliminary evidence of IMGN853 antitumor activity
- Characterize the immunogenicity of IMGN853

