2.2.2. Secondary

Secondary endpoints include:

- Treatment-emergent adverse events (TEAEs) and clinically significant \geq Grade 3 changes in laboratory test results, physical examination, ECGs or vital signs
- Treatment-emergent ocular adverse events
- PK parameters: C_{max} , AUC, terminal half-life ($t_{1/2}$), clearance (Cl), volume of distribution at steady state (Vss), T_{max} , AUC
- Number of patients with RECIST 1.1 criteria (see [Protocol Appendix E](#)) clinical responses and/or number of patients with GCIG Cancer Antigen 125 (CA-125) criteria clinical responses (see [Protocol Appendix F](#))
 - Objective response rate (ORR; MTD Expansion Cohorts # 1 and 2)
 - Duration of response (DOR)
 - Progression-free survival (PFS)
 - Time-to-progression (TTP)
- Human Anti-Drug Antibody (HADA) and Human Anti-Human Antibody (HAHA) levels

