- TEAEs leading to drug withdrawal. This subset includes TEAEs with an Action Taken of “Drug Permanently Discontinued.”
- Related TEAEs leading to drug withdrawal.
- TEAEs leading to dose delay.
- TEAEs leading to dose reduction.
- TEAEs leading to dose delay or dose reduction.
- Related TEAEs leading to dose delay.
- Related TEAEs leading to dose reduction.
- Related TEAEs leading to dose delay or dose reduction.
- All deaths as well as deaths on Study or within 28 Days of the Last Dose
- Treatment related TEAEs leading to death on study or within 28 days of Last Dose
- Ocular TEAEs
 - Incidence and CTCAE grade of ocular TEAEs
 - Time to first onset of ocular TEAEs
 - Action taken (none, interruption, dose reduction or delay, discontinuation) due to ocular TEAEs
- Peripheral Neuropathy

Subgroup analyses of TEAEs for the patients in EOC expansion cohorts (cohorts 1, 3, and 5) will be performed on the following patient subgroups:

- Patients in EOC expansion cohorts 1, 3, and 5 by platinum resistant status (platinum resistant vs platinum sensitive).
- Patients who are platinum resistant in EOC expansion cohorts 1, 3, and 5 by number of prior regimens (1-3 vs >3).
- Patients who are platinum resistant in EOC expansion cohorts 1, 3, and 5 by FR α percent staining at intensity 2+ (PS2) (25-49%, 50-74%, 75-100%, 50 – 100%).

In addition, TEAEs and related TEAEs will be summarized for patients in EOC expansion cohorts (1, 3, and 5) who are platinum resistant and who have received 1-3 prior lines of therapy and whose FR α percent staining at intensity 2+ (PS2) is 50-100%.

The following AE listings will be produced:

- All pre-treatment AEs will be listed.
- All AEs, sorted by cohort and chronologically within patient. This listing includes system organ class, preferred term, onset and end dates, and other relevant information.
- Serious TEAEs, sorted by cohort and chronologically within patient.
- TEAEs leading to drug withdrawal. This subset includes TEAEs with an Action Taken of “Drug Permanently Discontinued.”
- TEAEs related to study drug. This listing will include TEAEs with a drug relationship of “Possibly Related” or “Definitely Related.” It will also include TEAEs with missing drug relationships.
- Serious TEAEs related to study drug. This listing will include serious TEAEs with a drug relationship of “Possibly Related” or “Definitely Related.” It will also include serious TEAEs with missing drug relationships.

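### The eye-drop objective rests mainly on crude percentages of patients with an ocular event, not linked to time on drug, so unequal exposure could mimic or hide an effect of the drops.

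*SAP*

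**What the plan says.** SAP 2.1.2 sets the objective: "Evaluate the effectiveness of primary, prophylactic steroid eye drops in preventing or lessening keratopathy and/or blurred vision". The matching endpoint in SAP 2.2.2 is "Treatment-emergent ocular adverse events".

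SAP 6.2 counts an event as treatment-emergent from first dose to 28 days after the last dose. Its tables give counts and percentages of patients with at least one such event. Three ocular outputs are listed: "Incidence and CTCAE grade of ocular TEAEs", time to first onset, and action taken. No estimator, censoring rule or comparison group is given for time to first onset. The TEAE subgroup analyses of Cohorts 1, 3 and 5 are by platinum status, prior regimens and receptor staining; none contrasts drops with no drops. SAP 6.1 summarizes doses, cycles and duration of dosing separately.

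Protocol Appendix A, footnote h, states: "Ocular symptom assessment will be performed prior to the start of each cycle by the treating physician or other qualified individual". SAP 6.11 handles these data in one line: "Results of the Ocular Assessments will be presented in data listings".

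The only quantitative statement on the drops is in Protocol 11.1: for a fall in blurred vision from 50% to 30% with 40 patients, power is "68% using one-sided alpha of 20% and Chi-Square test statistics". The SAP does not carry this over, and the protocol synopsis says there is no formal hypothesis testing.

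**The concern.** Treatment has no fixed length (Protocol 4.1.1), so each patient's window for a first ocular event depends on how long she stays on drug. The percentage ever affected mixes the risk per cycle with the number of cycles.

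The ovarian cohorts are not the same population. Cohort 1 is platinum-resistant with at most five prior regimens, Cohort 3 has no upper limit, and Cohort 5 is relapsed disease with three or four (Protocol 3.1). Their time on drug may differ. If it does, the crude percentages will differ even if the drops do nothing, or may look alike when the drops work. Since no test is planned, these descriptive tables are what a reader will use to judge the objective.

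Time to first onset could correct for exposure, but only if patients without an event contribute follow-up time. A summary restricted to patients with an event would not. The by-cycle symptom data, which have a natural denominator of patients assessed, are not summarized.

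**Working it through.** **1. The protocol's own figure.** Inputs from Protocol 11.1: p1 = 0.50, p2 = 0.30, one-sided alpha 0.20 (z = 0.8416), chi-square test. Power = Φ{[0.20 − z·√(2·0.4·0.6/n)] / √[(0.25 + 0.21)/n]}, with n per group.

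- n = 20: (0.20 − 0.8416 × 0.1549)/0.1517 = 0.459, power 67.7%. This reproduces the stated 68%.
- n = 40: (0.20 − 0.8416 × 0.1095)/0.1072 = 1.005, power 84.3%.

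The 68% therefore fits 20 per group, although Cohort 5 has 40 patients who all receive drops. The groups behind the figure are not named. Either way it compares two crude proportions and has no exposure term.

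**2. What unequal exposure does to a crude percentage.** The documents give no cycles per cohort and no per-cycle risk, so this is an illustration. Assume the same constant per-cycle risk h in both cohorts, no effect of the drops, and 50% affected in the comparator after m cycles. Then (1 − h)^m = 0.5. A cohort with k cycles shows 1 − 0.5^r, where r = k/m. Only the ratio of cycles matters.

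The last column is the chance that a one-sided 20% chi-square comparison of 40 with 40 would favour the cohort with fewer cycles, by the same normal approximation.

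| r | crude incidence | chance of an apparent benefit |
|---|---|---|
| 1 | 50.0% | 20.0% |
| 5/6 | 43.9% | 38.5% |
| 4/6 | 37.0% | 63.1% |
| 3/6 | 29.3% | 85.9% |

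The full fall from 50% to 30% appears at r = ln 0.7 / ln 0.5 = 0.515, for example 3.1 cycles against 6, or 2.1 against 4.

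**3. The other direction.** With r = 7/5 the crude incidence is 1 − 0.5^1.4 = 62.1%, and drops with no effect would look harmful. If the drops truly gave 30% at equal exposure, 1/0.515 = 1.94 times the comparator's cycles would bring Cohort 5 back to 50% and hide the effect.

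**4. What a censored estimate does.** Under the same assumptions with m = 6, h = 1 − 0.5^(1/6) = 10.9%. Cumulative incidence is then 20.6% after two cycles, 37.0% after four and 50.0% after six, in any cohort, however long its patients stay on drug. An estimate that censors patients without an event targets these values.

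**The case against.** Four points against pressing this harder are fair.

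- **The objective is not confined to crude percentages.** SAP 6.2 also plans grade, time to first onset and action taken. SAP 6.1 reports cycles and duration, and SAP 3.8 makes cohort or treatment group the default column, so a gross difference in exposure would be visible. This stands. But visible is not adjusted: grade and action taken are not linked to exposure, and time to first onset has no method.
- **A reader might infer that time to first onset covers only patients with an event.** That would be a reading of silence. Where the plan restricts a time variable in that way, it says so, as for time to response (SAP 5.1.6) and time to seroconversion (section 2.2.2 of the PK and immunogenicity analysis plan). Table shells are in a separate document. The fair statement is that the method is unspecified.
- **A reader might infer that the symptom check is the only uniform ocular data source.** It is not. Protocol Appendix A schedules AE assessment for all patients on Day 1 of every cycle and at other visits. Protocol 9.1.1.1 lets AEs be found by questioning, so symptoms from the check can reach the TEAE tables. What is still missing is a by-cycle summary with the number assessed as denominator.
- **The illustration rests on assumptions.** Constant risk is doubtful: the protocol ties ocular events to peak concentration (1.10.1, 1.10.2), and dosing is held for some ocular symptoms (5.8.8). Reproducing the whole planned effect needs about half the comparator's cycles. This limits the size that can be claimed, not the mechanism.

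Exposure adjustment also cannot make non-randomized cohorts comparable.

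**Conclusion.** The concern holds as a gap in specification. The main planned measure for the eye-drop objective depends on time on drug, nothing in the SAP links it to exposure, the one output that could correct for this has no stated method, and the by-cycle symptom data are only listed.

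The size is illustrative. With equal constant per-cycle risk and 50% affected in the comparator, about 51% of the comparator's cycles yields 30% with no effect of the drops; 5/6 of the cycles yields 43.9%.

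A reader might go further and conclude that Cohort 5 will have fewer cycles, so that the drops will look protective. The documents do not support that. They give no cycles per cohort, the limits on prior regimens overlap, and the bias can run either way.

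The change is worth making because it uses data already collected and SAP 1.1 allows modification until database lock.

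**What to change.** **SAP 6.2.** Define time to first onset as Kaplan-Meier cumulative incidence of first blurred vision and, separately, first keratopathy. Report it for Cohort 5 and for the named comparators, Cohorts 1 and 3, which receive no prophylactic drops. Give estimates with 95% CIs at the end of Cycles 2, 4 and 6 (nominally days 42, 84 and 126 with 21-day cycles). Censor patients without an event at the end of the TEAE window, 28 days after the last dose. Keep the incidence and grade table.

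**SAP 6.11.** Keep the listing and add a table by cohort and cycle of patients with ocular symptoms, with the number assessed as denominator. Note beneath it that patients who stopped treatment, including any who stopped for ocular toxicity, leave that denominator.

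**Interpretation.** State in the SAP that the comparison is non-randomized and descriptive, and that allowing for exposure does not remove differences between the cohort populations.

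**Cost.** One extra table and one Kaplan-Meier output, with no new procedures or data collection.

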6.12. Transfusions

All blood product transfusions recorded on the concomitant procedure or concomitant medication eCRF will be presented in data listings.

6.13. Physical Examination

Physical Examination results will be presented in data listings.

6.14. Pulmonary Function Tests

Pulmonary Function Test results will be presented in data listings.

6.15. Eastern Cooperative Oncology Group Performance Status (ECOG PS)

Eastern Cooperative Oncology Group performance status (ECOG PS) results will be presented in data listings.

6.16. FACT/GOG Neurotoxicity Questionnaire

Data from the Functional Assessment of Cancer Therapy, Gynecologic Oncology Group (FACT/GOG) Questionnaire will be reported in data listings.

7. PHARMACOKINETIC AND PHARMACODYNAMIC ANALYSES

The PK analyses for this study will be covered by a separate, independent analysis plan prepared by the PK analysis vendor in collaboration with ImmunoGen.

T_{\max}	Time at Which C_{\max} Occurs
V_{ss}	Volume of Distribution at Steady State
Wx3Q4W	Dosing on Day 1, 8, 15, with Cycles Repeating Every 28 Days

1. OVERVIEW AND INVESTIGATIONAL PLAN/PURPOSE

This analysis plan provides a description of the strategy and techniques to be used to analyze pharmacokinetic (PK) and immunogenicity data for the mirvetuximab soravtansine (IMGN853) 0401 study.

[figure not shown]
1.1. Study Design

This was an open label, Phase 1, non-randomized, first in human (FIH) study of IMGN853 in adult patients with FOLR1-positive solid tumors that have relapsed, or are refractory to standard therapies. Two dosing schedules were evaluated in this study:

Schedule A: IMGN853 administered on Day 1, with cycles repeating every three weeks (Q3W)

The dose escalation phase initially enrolled 1 patient each at the first four dose levels. Patients were enrolled in subsequent cohorts using a standard 3+3 design, with each cohort consisting of 3 or 4 up to 6 patients.

Schedule B: IMGN853 administered on Days 1, 8, and 15, with cycles repeating every 28 days (modified weekly)

1.2. Pharmacokinetic and Immunogenicity Analysis Objectives

The objective of this analysis is to characterize the PK and immunogenicity of IMGN853.

1.3. PK Sampling Schedule

1.3.1. Schedule A

Blood samples for PK measurements were taken at the following time points:

Cycles 1 and 3:

Day 1 – Pre-dose, immediately following completion of infusion (+10 minutes), 2 hours (± 10 minutes) following the completion of infusion, 4 hours (± 10 minutes) following the completion of infusion, 6 hours (± 10 minutes) following the completion of infusion and 8 hours (± 10 minutes) following the completion of infusion

NOTE: 8 hours and 6 hours following the completion of infusion were not required for all patients

Day 2 – 24 hours after completion of infusion (± 2 hours)

Day 3 – 48 hours after completion of infusion (± 2 hours)

Day 4 or 5 – a single blood sample for PK (± 24 hours)

Day 8 – a single blood sample for PK (± 24 hours)

Day 15 – a single blood sample for PK (± 24 hours)

Cycles 2 and 4 through 6:

Day 1 – Pre-dose and immediately following completion of infusion (+10 minutes)

End of Treatment

28 Day Follow Up

1.3.2. Schedule B

Blood samples for PK measurements were taken in at the following time points:

Cycles 1 and 3:

Day 1 – Pre-dose, immediately following completion of infusion (+10 minutes), 2 hours (± 10 minutes) following the completion of infusion, and 4 hours (± 10 minutes) following the completion of infusion

Day 2 – 24 hours after completion of infusion (± 2 hours)

Day 8 – Pre-dose and immediately following completion of infusion (+10 minutes)

Day 15 – Pre-dose, immediately following completion of infusion (+10 minutes), 2 hours (± 10 minutes) following the completion of infusion, and 4 hours (± 10 minutes) following the completion of infusion

Day 16 – 24 hours after completion of infusion (± 2 hours)

Day 22 – a single blood sample for PK (± 24 hours)

Cycles 2 and 4 through 6:

Day 1 – Pre-dose and immediately following completion of infusion (+10 minutes)

End of Treatment**28 Day Follow Up****1.3.3. Additional Samples**

Per study protocol, any patient who experienced a Grade 2 or greater infusion reaction during the administration of IMGN853 had blood drawn within 3 hours of the onset of the reaction and one week later for determination of drug concentration and antibodies to IMGN853.

PK samples were also obtained, as feasible, any time during the treatment period for assessment of study drug related SAEs if deemed appropriate by the Investigator and Sponsor.

1.3.4. Bioanalysis of PK Samples

The following table summarizes the bioanalytical methodology used to quantitate IMGN853, total antibody, and free payload (DM4 and s-methyl DM4).

Analyte	Method	Lower Limit of Quantitation	CRO Validation Report Number
IMGN853	ELISA	75.0 ng/mL	REYB2, REGD2
Total Antibody	ELISA	500 ng/mL	REYN2, REGE2
DM4, S-methyl-DM4	LC-MS	0.100 ng/mL	REGC2

ELISA, enzyme linked immunosorbent assay; LC-MS, liquid chromatography-mass spectrometry.

1.4. Immunogenicity Assessments

Assessments for immunogenicity against IMGN853 were performed on plasma samples collected for PK assessments. This included samples collected prior to infusion on Day 1 of Cycles 1, 2, 4, and 5, at the End of Treatment and at Follow-up visits. The current analysis will evaluate the potential impact of immunogenicity on PK of IMGN853 and total M9346A antibody, specifically comparing IMGN853 and total antibody exposure between the immune positive and immune negative populations.

1.4.1. Bioanalysis of Immunogenicity Samples

An electrochemiluminescent method was used for the detection of anti-IMGN853 antibodies in plasma from samples collected into either sodium heparin or K₂EDTA tubes (respective validation reports: REYO2 and REGG2). The qualitative assay was designed to detect anti-IMGN853 antibodies in human plasma. Samples with a signal response above the fixed cut point were classified as potentially positive, while those below the cut point were classified as negative. Potentially positive samples were confirmed in the Tier 2 screening assay, where conjugate was added as an inhibition solution. Samples were confirmed positive if the percent inhibition was $\geq 29.1\%$ for sodium heparin samples and 30.2% for K₂EDTA samples. In Tier 3, the confirmed positive samples were titered until a negative response was obtained and the sample titer was reported as the reciprocal of the last dilution that produced a response above the cut point.

